#### 2.4.4.2.3.5 Change from baseline in total score of St George Respiratory Questionnaire (SGRQ) endpoint

The absolute change from baseline in SGRQ total score endpoint will be analyzed on the mITT population. Assessments at week 52 will be used regardless of whether the patient has previously discontinued treatment. No imputation will be performed for the week 52 missing values of SGRQ total score. Only patients having a baseline and a post-baseline total SGRQ score values in at least one time points analysis window will be considered in the analysis.

The absolute change from baseline in SGRQ total score at 52 weeks will be analysed using a Mixed Model with Repeated Measures (MMRM) with the fixed categorical effects of treatment arm, stratification factor (with/without Background Therapy), time point, treatment-by-time point interaction, stratification factor-by-treatment-by-time point interaction, as well as the continuous fixed covariate of SGRQ total score at baseline will be used. Parameters will be estimated with the Newton-Raphson algorithm, an unstructured covariance matrix will model the within-patient errors, and the denominator degrees of freedom will be estimated using Satterthwaite's approximation.

The SAR156597 qw arm will be tested versus Placebo at a type I error level of 10% first and if significant, will the SAR156597 q2w arm be tested versus Placebo at a two-sided type I error level of 10% using the appropriate contrast. The adjusted Least Square Means (LSMeans) estimates and standard errors (SE) will be provided for each of the 3 arms, adjusted differences of means (LSMEAN differences), corresponding standard errors (SE) and 90% CIs will be assessed for each active arm versus placebo.

For each component score (Symptoms, Activity, Impacts) and the SGRQ total score, descriptive statistics for values and changes from baseline will be described over time by treatment arm and by background therapy status. The mean (SD) of each score values and the mean (SD) absolute change from baseline in each score over time will be graphically represented by treatment arm and by background therapy status.

The representation of LSmeans (SE) over time will be displayed by treatment arm and background therapy status for the SGRQ total score.

#### 2.4.4.2.3.6 Change from baseline in total score of EuroQol Questionnaire, 5 level system (EQ-5D-5L) endpoint

The absolute change from baseline in EQ-5D-5L total score endpoint will be analyzed on the mITT population. Assessments at week 52 will be used regardless of whether the patient has previously discontinued treatment. No imputation will be performed for the week 52 missing values of EQ-5D-5L total score. Only patients having a baseline and a post-baseline EQ-5D-5L total score values in at least one time points analysis window will be considered in the analysis.

The absolute change from baseline in EQ-5D-5L total score at 52 weeks will be analysed using a Mixed Model with Repeated Measures (MMRM) with the fixed categorical effects of treatment arm, stratification factor (with/without Background Therapy), time point, treatment-by-time point interaction, stratification factor-by-treatment-by-time point interaction, as well as the continuous fixed covariate of EQ-5D-5L total score at baseline will be used. Parameters will be estimated with the Newton-Raphson algorithm, an unstructured covariance matrix will model the within-patient errors, and the denominator degrees of freedom will be estimated using Satterthwaite's approximation.

The SAR156597 qw arm will be tested versus Placebo at a type I error level of 10% first and if significant, will the SAR156597 q2w arm be tested versus Placebo at a two-sided type I error level of 10% using the appropriate contrast. The adjusted Least Square Means (LSMeans) estimates and standard errors (SE) will be provided for each of the 3 arms, adjusted differences of means (LSMEAN differences), corresponding standard errors (SE) and 90% CIs will be assessed for each active arm versus placebo.

For EQ-5D-5L VAS and the EQ-5D-5L total score, descriptive statistics for values and changes from baseline will be described over time by treatment arm and by background therapy status. The mean (SD) of each score values and the mean (SD) absolute change from baseline in each score over time will be graphically represented by treatment arm and by background therapy status.

The representation of LSmeans (SE) over time will be displayed by treatment arm and background therapy status for the EQ-5D-5L total score.

#### **2.4.4.3 Multiplicity issues**

The overall type I error rate for this study is 5%. For the primary endpoint, a hierarchical testing procedure will be used to control the type I error over the two doses. The SAR156597 qw arm will be compared to placebo first, and only if this comparison is significant will the SAR156597 q2w arm be compared to placebo.

The same procedure will be used for the disease progression endpoint if significance is achieved for both doses on the primary endpoint.

For other secondary endpoints considered exploratory, a hierarchical testing procedure will be used to control the type I error over the two doses. The SAR156597 qw arm will be compared to

placebo first at a two-sided type I error level of 10%, and only if this comparison is significant will the SAR156597 q2w arm be compared to placebo at a two-sided error level of 10%.

#### **2.4.4.4 Additional efficacy analysis**

##### *2.4.4.4.1 Absolute change from baseline in % predicted DLCO*

The absolute change from baseline in % predicted DLCO endpoint will be analyzed on the mITT population. Assessments at week 52 will be used regardless of whether the patient has previously discontinued treatment. No imputation will be performed for the week 52 missing values of %predicted DLCO. Only patients having a baseline and a post-baseline % predicted DLCO values in at least one time points analysis window will be considered in the analysis.

The absolute change from baseline in % predicted DLCO at 52 weeks will be analyzed using a Mixed Model with Repeated Measures (MMRM) with the fixed categorical effects of treatment arm, stratification factor (with/without Background Therapy), time point, treatment-by-time point interaction, stratification factor-by-treatment-by-time point interaction, as well as the continuous fixed covariate of % predicted DLCO baseline. Parameters will be estimated with the Newton-Raphson algorithm, an unstructured covariance matrix will model the within-patient errors, and the denominator degrees of freedom will be estimated using Satterthwaite's approximation.

The SAR156597 qw arm will be tested versus Placebo at a type I error level of 10% first and if significant, will the SAR156597 q2w arm be tested versus Placebo at a two-sided type I error level of 10% using the appropriate contrast. The adjusted Least Square Means (LSMeans) estimates and standard errors (SE) will be provided for each of the 3 arms, adjusted differences of means (LSMEAN differences), corresponding standard errors (SE) and 90% CIs will be assessed for each active arm versus placebo.

Descriptive statistics for values and changes from baseline will be presented by treatment arm and background therapy status for each time point. The mean (SD) % predicted DLCO values and the mean (SD) absolute change from baseline in % predicted DLCO over time will be graphically represented by treatment arm and by background therapy status. The representation of LSmeans (SE) over time will be displayed by treatment arm and background therapy status.

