10.3.4 Handling of patients after permanent treatment discontinuation

Patients will be followed-up according to the study procedures as specified in this protocol up to the scheduled date of study completion, or up to recovery or stabilization of any AE to be followed-up as specified in this protocol, whichever comes last.

If possible, and after the permanent discontinuation of treatment, the patients will be assessed using the procedure normally planned for the last dosing day with the IMP (End of treatment visit/Visit 9) and then will be asked to come to the scheduled on site visits for safety monitoring and respiratory function assessment (FVC and DLCO).

All cases of permanent treatment discontinuation should be recorded by the Investigator in the appropriate pages of the e-CRF when considered as confirmed.

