### **2.1.3 Efficacy endpoints**

Unless otherwise specified, all efficacy parameters values (scheduled or unscheduled) may be used to provide a value for the primary and secondary efficacy endpoints.

For FVC, FEV1 and FEV1/FVC parameters, a value is considered valid if this is an ATSBEST value with a grade “A” or “B” and a status “CLEAN” or “MANUAL”.

All measurements (scheduled or unscheduled) will be assigned to analysis windows defined in [Table 6](#), in order to provide an assessment of the efficacy parameter at each time point planned to be collected as per protocol. For all post-baseline time points, the value used for the analyses at a given time point (e.g at week 52) is the valid value obtained within the corresponding analysis window. If multiple valid values of a variable exist within an analysis window, the nearest from the targeted study day will be selected. In case of ties, the best value will be considered.

The baseline value is the last available and valid measurement obtained before or equal to the date and time of the first double-blind IMP injection. For patients randomized and not treated, the baseline value is defined as the last available and valid value obtained before or equal to the date and time of randomization.

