- ii. Other patients (patients in active arm and not taking treatment at 52 weeks; or patients in placebo arm): Missing values at 52 weeks will be imputed using a model estimated from the subset of patients in the placebo arm who completed the 52-week treatment period and with a week 52 value. The imputation model will be based on a Mixed Model with Repeated Measures (MMRM) with fixed categorical effect of stratification factor (with/without Background Therapy) and repeated categorical effect for time point (baseline, week 12, week 24, week 36, week 52). Parameters will be estimated with the Newton-Raphson algorithm, an unstructured covariance matrix will model the within-patient errors, and the denominator degrees of freedom will be estimated using

- Satterthwaite's approximation. Missing values at 52 weeks will be imputed using the empirical best linear unbiased prediction (EBLUP).
- iii. When running the imputation model, if the predicted absolute change from baseline calculated from the predicted week 52 value is greater than zero (increases above baseline), it will be set to zero.
  - iv. The non-monotone missing patterns with a week 52 value available will not be imputed.
- b) Week 52 missing values due to lung transplant:
    - i. Any % predicted FVC value assessed after a lung transplant will be considered as missing.
    - ii. No imputation of a week 52 value for % predicted FVC. In step 2, patients will be ranked worse than missing data due to reasons other than death or lung transplant.
  - c) Week 52 missing values due to death :
    - i. No imputation of a week 52 value for % predicted FVC. In step 2, patients will be ranked worse than missing data due to lung transplant.
2. Rank ANCOVA
- a) Ranking within each stratum of the stratification factor (with/without Background Therapy)
    - i. Death: Missing data due to death will be ranked based on a time-to-death, with shortest time until death as the worst (lowest) rank (from 1 to  $n_{\text{stratum,death}}$ ).
    - ii. Lung transplant: Missing data due to lung transplant will be ranked based on a time-to-lung transplant, with shortest time until lung transplant as the worst (lowest) rank (from  $n_{\text{stratum,death}}+1$  to  $n_{\text{stratum,death}}+n_{\text{stratum,lungtransplant}}$ ). So, missing data due to lung transplant will be less penalized than deaths.

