#### 2.4.4.2.3.3 Change from baseline in 6-MWT distance endpoint

The absolute change from baseline in 6-MWT distance endpoint will be analyzed on the mITT population. Assessments at week 52 will be used regardless of whether the patient has previously discontinued treatment. No imputation will be performed for the week 52 missing values of 6-MWT distance. Only patients having a baseline and a post-baseline 6-MWT distance values in at least one time points analysis window will be considered in the analysis.

The absolute change from baseline in 6-MWT distance at 52 weeks will be analysed using a Mixed Model with Repeated Measures (MMRM) with the fixed categorical effects of treatment arm, stratification factor (with/without Background Therapy), time point, treatment-by-time point interaction, stratification factor-by-treatment-by-time point interaction, supplemental oxygen use (Yes/No answer to the “Does the subject need oxygen therapy” question on the “Idiopathic Pulmonary Fibrosis History” e-CRF page) recorded at baseline, as well as the continuous fixed covariate of 6-MWT distance at baseline will be used. Parameters will be estimated with the Newton-Raphson algorithm, an unstructured covariance matrix will model the within-patient errors, and the denominator degrees of freedom will be estimated using Satterthwaite’s approximation.

The SAR156597 qw arm will be tested versus Placebo at a type I error level of 10% first and if significant, will the SAR156597 q2w arm be tested versus Placebo at a two-sided type I error level of 10% using the appropriate contrast. The adjusted Least Square Means (LSMeans) estimates and standard errors (SE) will be provided for each of the 3 arms, adjusted differences of means (LSMEAN differences), corresponding standard errors (SE) and 90% CIs will be assessed for each active arm versus placebo.

Descriptive statistics for values and changes from baseline in 6-MWT distance in the mITT population will be presented by treatment arm and background therapy status for each time point. The mean (SD) 6-MWT distance values and the mean (SD) absolute change from baseline in 6MWT distance over time will be graphically represented by treatment arm and by background therapy status.

The representation of LSmeans (SE) over time will be displayed by treatment arm and background therapy status.

In addition, to assess the quality of data:

- the number (%) of patients having a completed 6 minute walking test,

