#### 2.4.4.2.3.4 Change from baseline in HRCT lung interstitial score endpoint

The absolute change from baseline in HRCT lung interstitial score endpoint will be analyzed on the mITT population. Assessments at week 52 will be used regardless of whether the patient has previously discontinued treatment. No imputation will be performed for the week 52 missing values of HRCT lung interstitial scores. Only patients having both the baseline and week 52 Total Fibrosing ILD score assessments available will be considered in the analysis.

The change from baseline at 52 weeks in Total Fibrosing ILD score will be analyzed using an ANCOVA model with fixed effect for treatment arm, adjusted on baseline Total Fibrosing ILD score, Emphysema total score at baseline, and the stratification factor (with/without Background Therapy) covariates, with a stratification factor-by-treatment interaction will be performed. The SAR156597 qw arm will be tested versus Placebo at a two-sided type I error level of 10% first and if significant, will the SAR156597 q2w arm be tested versus Placebo at a two-sided type I error level of 10% using the appropriate contrast. The adjusted Least Square Means (LSMeans) and their 90% CIs will be assessed for each treatment arm.

Descriptive statistics for values and changes from baseline in Total Fibrosing ILD score will be described over time by treatment arm and by background therapy status. The mean (SD) Total Fibrosing ILD score values and the mean (SD) absolute change from baseline in Total Fibrosing

ILD score over time will be graphically represented by treatment arm and by background therapy status.

The representation of LSmeans (SE) over time will be displayed by treatment arm and background therapy status for the Total Fibrosing ILD score.

In addition, descriptive statistics for values and changes from baseline in pattern score and the Emphysema total score will be described over time by treatment arm and by background therapy status. The mean (SD) scores values and the mean (SD) absolute change from baseline in scores over time will be graphically represented by treatment arm and by background therapy status.

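### The SAP discards post-transplant values only for % predicted FVC; by default a recorded post-transplant DLCO or HRCT fibrosis score would be analysed as observed and could count as improvement

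*SAP*

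**What the plan says.** **FVC.** Step 1b(i) of the primary analysis (SAP 2.4.4.1) reads: "Any % predicted FVC value assessed after a lung transplant will be considered as missing". The patient is then ranked below every patient with an observed or imputed change and above the deaths.

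**Default for efficacy values.** SAP 2.1.3 says that, unless otherwise specified, "all efficacy parameters values (scheduled or unscheduled) may be used to provide a value for the primary and secondary efficacy endpoints". It then assigns all measurements to the analysis windows of Table 6, where Week 52 runs from Day 309 to Day 406.

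**DLCO and HRCT.** SAP 2.4.4.4.1 (DLCO, an MMRM) and SAP 2.4.4.2.3.4 (Total Fibrosing ILD score, an ANCOVA) share one data-use sentence: "Assessments at week 52 will be used regardless of whether the patient has previously discontinued treatment". On missing data, the first says "No imputation will be performed for the week 52 missing values of %predicted DLCO" and the second "No imputation will be performed for the week 52 missing values of HRCT lung interstitial scores". Neither mentions transplant. Nor do the sections on 6-MWT, SGRQ and EQ-5D-5L, which follow the same pattern (for 6-MWT, "No imputation will be performed for the week 52 missing values of 6-MWT distance").

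**Transplant elsewhere in the SAP.** It is a disease-progression event (2.1.3.2.2), and Table 3 counts it as an event for all-cause mortality. In sensitivity analysis 1 the imputed FVC of a transplanted patient cannot exceed that patient's last available value.

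**Collection.** After permanent treatment discontinuation, Protocol 10.3.4 has patients "asked to come to the scheduled on site visits for safety monitoring and respiratory function assessment (FVC and DLCO").

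**The concern.** Step 1b(i) is needed only if lung function may be recorded after a transplant and should not be read as the course of the patient's IPF. That reasoning applies equally to DLCO and to a CT fibrosis score, which after a transplant describe donor lung in whole or in part. Yet the rule stops at FVC.

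The same event would then be near-worst on the primary endpoint and a progression event on the key secondary endpoint, while it could appear as a gain in DLCO or a fall in fibrosis score. Such a gain would favour the arm with more transplants. Both endpoints carry a formal two-sided 10% test, qw before q2w (SAP 2.4.4.3 and the endpoint sections). Table 1 of the SAP says the Week 52 analysis will inform the decision to move to Phase 3. Without a rule set beforehand, the handling of one or two influential patients could be decided after unblinding.

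**Working it through.** **1. What the text leads to.** The FVC rule names FVC only. SAP 2.1.3 admits values unless something else is specified, and nothing else is specified for DLCO or HRCT. The shared data-use sentence concerns stopping treatment, so it does not remove a post-transplant value. A programmer following the SAP would therefore include one that was recorded. In the DLCO MMRM this applies at every visit after the transplant, not only Week 52.

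**2. Can such values exist?** Protocol 10.3 asks that patients stay in the study as long as possible, and Protocol 4.2.1 plans 52 weeks of follow-up after discontinuation. DLCO is one of the two tests named in Protocol 10.3.4, so the gap is clearest there. For HRCT it is less certain. Visit 9 includes the scan (Protocol 10.1.8) and its procedures are requested at discontinuation, which could fall before or after the transplant.

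**3. Size.** The documents give no figure on this point: no transplant count, no post-transplant values, and no SD for DLCO or HRCT change. All inputs below are assumptions. Take n = 80 evaluable patients per arm and one transplant, in one arm only. Let *d* be that patient's distance from the mean of the rest of the arm and *s* the SD of change. The contrast is a simple unadjusted difference in means.

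- Shift in the contrast = *d*/80
- Variance in the affected arm ≈ *s*² + *d*²/80
- SE of the contrast ≈ √[(*s*² + *d*²/80 + *s*²)/80]

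| Case | Shift | SE of contrast | Shift/SE |
|---|---|---|---|
| DLCO, *d* = +35, *s* = 10 | 35/80 = 0.44 | √[(115.3 + 100)/80] = 1.64 | 0.27 |
| HRCT, *d* = −40, *s* = 5 | 40/80 = 0.50 | √[(45 + 25)/80] = 0.94 | 0.53 |
| HRCT, *d* = −25, *s* = 5 | 25/80 = 0.31 | √[(32.8 + 25)/80] = 0.85 | 0.37 |
| HRCT, *d* = −40, *s* = 8 | 40/80 = 0.50 | √[(84 + 64)/80] = 1.36 | 0.37 |

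The comparison is with the SE of the between-arm difference, because that is what is tested. Using the SE of one arm mean without the outlier would give 0.44/1.12 = 0.4 for DLCO and 0.50/0.56 = 0.9 for the first HRCT row, which overstates the effect.

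**4. Effect on the 10% test.** This is a second illustration, with 100 patients per arm, a mean change of −5 in the others, and an SD of 12 borrowed from the FVC assumption in SAP 1.3. There is no true difference, all transplants fall in one arm, and the post-transplant change ranges from 0 to +40 points. The two-sided 10% test rejects in:

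- 10.0–11.1% of trials with one transplant
- 10.1–18.8% with three
- 10.4–31.5% with five

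**5. Would the patient be an extreme improver?** Under the same N(−5, 12) assumption the top 10% of changes starts at −5 + 1.28 × 12 ≈ +10.4. A post-transplant change of 0 lies at the 66th percentile, +10 at the 89th and +20 at the 98th.

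**The case against.** **Silence is not a rule.** No sentence says post-transplant values will be used, and the shared data-use sentence is about treatment discontinuation. That is correct. What remains is the default in SAP 2.1.3, which would let them in.

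**The size and direction of change are not in the documents.** A reader might infer that a transplanted patient becomes one of the largest improvers. The documents give neither the size nor the direction of change after transplant, so all they support is that the value could count as improvement.

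**Transplants should be few.** Exclusion E09 removes patients who are listed, or expected to be listed within 6 months. This limits the likely effect but does not rule out later transplants in a 52-week trial.

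**Collection outside DLCO is uncertain.** Protocol 10.3.4 names only FVC and DLCO, with safety, at later visits, although it also says follow-up is according to the study procedures. For HRCT, SAP 2.1.3.2.8 allows regions to be recorded as not available, gives no score with fewer than four of six regions, and leaves the German Week 52 scan to the investigator. None of these provisions mentions transplant, so they may not remove such a scan.

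**One could also infer that all five endpoints need the FVC rule.** For walk distance and quality of life, keeping what the patient achieved or reported is a defensible treatment-policy choice. The documents do not show it to be wrong.

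**The outlier also widens the SE,** which partly offsets the shift. The table in the working includes this.

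**Conclusion.** The gap is real and narrow. The SAP's post-transplant rule covers % predicted FVC only. As written, a recorded post-transplant % predicted DLCO or Total Fibrosing ILD score would be analysed as observed and could count as improvement, against the SAP's own treatment of transplant elsewhere. The case is firmest for DLCO, where later measurement is expressly planned.

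On the stated assumptions one transplant moves the contrast by about 0.27 SE for DLCO and roughly 0.4 to 0.5 SE for HRCT. A larger effect needs several transplants concentrated in one arm, and with none there is no effect.

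The endpoints are exploratory and tested at 10%. The primary and disease-progression analyses already count transplant as unfavourable, so their conclusions are not in question. The change is still worth making before unblinding, because it is small and extends the SAP's own logic.

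**What to change.** Extend step 1b(i), preferably by moving it to SAP 2.1.3 as a general rule. Any % predicted DLCO or HRCT score assessed after a lung transplant would be set to missing, as would any FVC value, and any FEV1 value where recorded, in the descriptive tables of SAP 2.4.4.4.2. Add a listing of transplanted patients with their post-transplant values. For 6-MWT, SGRQ and EQ-5D-5L, state in one sentence whether post-transplant values are kept or set to missing.

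The cost is a sentence or two and one listing, with no change to the sample size. The few transplanted patients would contribute only pre-transplant data. In the DLCO MMRM they would be treated as missing at random, not as near-worst as in the FVC ranking. In the HRCT ANCOVA, which needs both baseline and Week 52 scores, a patient whose only Week 52 scan is post-transplant would drop out. The fix therefore removes a possible spurious gain but does not penalise transplant on these endpoints, and the SAP should say so.
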